5.3.2 Dose Modifications

5.3.2.1 Cisplatin

Modifications of cisplatin for nephrotoxicity during radiotherapy are listed below. CrCl should be calculated using the Cockroft-Gault methodology. During radiation therapy, CrCl is to be recalculated each week, within 3 days of cisplatin administration.

Table 4: Dose modification of cisplatin dosing based on recalculation of the CrCl

Renal Function	Cisplatin Dosing
CrCl \geq 50:	35mg/m ²
CrCl \geq 40 but $<$ 50:	30mg/m ²
CrCl \geq 30 but $<$ 40	25mg/m ²
CrCl $<$ 30	Withhold dose

Dose increases for patients commenced at 30mg/m² are permitted should renal function improve (based on weekly recalculation of CrCl) during radiotherapy and after discussion with the study chair.

An FBE is to be performed within 3 days of each cisplatin administration. Modification parameters for cisplatin dose reduction are displayed below.

Table 5: Dose modification cisplatin based on neutrophil/platelet count

ANC	Platelet Count x10 ⁹		
	>150	75-149	<75
\geq 1.4	100%	100%	75%
0.8 – 1.4	100%	75%	75%
\leq 0.8	0%	0%	0%

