3.0 OBJECTIVES, HYPOTHESES & ENDPOINTS

3.1 Primary Objective, Hypothesis & Endpoints

Objective: To demonstrate that the addition of pembrolizumab to chemoradiotherapy for muscle invasive bladder cancer is feasible as measured by a satisfactorily low rate of unacceptable toxicity.

Hypothesis: Pembrolizumab in combination with chemoradiotherapy will be safe and well tolerated in patients with previously untreated muscle invasive bladder cancer.

Endpoints: Occurrence of an unacceptable toxicity affecting patients where an unacceptable toxicity is defined by any of the following:

- a) Occurrence of a grade 3 or 4 acute toxicity (excluding grade 3 or 4 urinary toxicity), occurring either during treatment or within 12 weeks after scheduled completion of treatment, or
- b) Cisplatin being withheld for \geq 2 doses
- c) Cisplatin doses being withheld or reduced such that <66% of the intended total cisplatin dose is delivered
- d) Radiation treatment being delayed beyond more than 7 weeks
- e) Any single pembrolizumab dose being delayed for more than 6 weeks. (Multiple dose delays will not be aggregated).

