5.3.1.3.1 Administration of cisplatin

Cisplatin chemotherapy will commence on the same day as radiation therapy. After 1000ml sodium chloride 0.9% is administered as prehydration (10mmol MgSO₄ is allowed to be added as per institutional preference), cisplatin 35mg/m² in 1000mL sodium chloride 0.9% will be administered over 60 minutes. Cisplatin is commercially available. Conceivably the co-administration of dexamethasone with the chemotherapy may reduce lymphocyte counts and efficacy of pembrolizumab. Therefore, the dose of dexamethasone administered with chemotherapy will be 4mg IV rather than 8mg unless \geq G2 nausea/vomiting develops. The 5HT3 antagonist palonosetron 0.25mg IV (or equivalent 5HT3 antagonist) will be given prior to cisplatin. Other antiemetic use such as aprepitant and/or olanzapine is permissible. Dexamethasone 4 mg IV premedication given prior to cisplatin is permitted and allowed to continue at dose \leq 4mg orally daily for 2 days after administration. Increase in dexamethasone dose is permitted in discussion with the principal investigator. Urine output measurement is not necessary before cisplatin administration as high urine flow does not appear to be protective.

Cisplatin will be administered weekly during radiotherapy at 7 day intervals

The chemotherapy is to be given preferably at the beginning of each week of treatment and as far as possible on the same day of the week (or within no more than 72 hours) on each occasion throughout the course of treatment.

No more than 6 doses of cisplatin will be administered.

Patients' renal function and myeloid function will be assessed within 72 hours prior to administration of each dose of cisplatin.

The patient should be assessed by the doctor prior to proceeding with each dose of chemotherapy.

Dose modification is described in 5.3.2.1.

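### Cisplatin Table 5 contradicts itself at ANC 0.8 (up to 100% in one row, 0% in the other), so a withheld-dose unacceptable toxicity can depend on which row is read

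*Combined protocol and SAP*

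**What the plan says.** Section 5.3.2.1 requires a blood count before every dose: "An FBE is to be performed within 3 days of each cisplatin administration". The result is then read against the grid headed "Table 5: Dose modification cisplatin based on neutrophil/platelet count". The three ANC rows are at or above 1.4, from 0.8 to 1.4, and at or below 0.8. The middle row reads "0.8 – 1.4 100% 75% 75" (per cent), and the bottom row is 0% in all three columns. The platelet columns are headed ">150 75-149 <75".

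Section 5.3.1.3.1 sets the number of administrations: "No more than 6 doses of cisplatin will be administered". Section 3.1 makes two cisplatin outcomes a UT, which is the primary endpoint event. One is "Cisplatin being withheld for \geq 2 doses", that is, two or more doses withheld. The other is "Cisplatin doses being withheld or reduced such that <66% of the intended total cisplatin dose is delivered". Section 8.1 repeats both and measures the total against the starting dose.

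**The concern.** Table 5 is a working rule, consulted up to six times per patient at five planned sites. At ANC 0.8 two sites could each follow the protocol faithfully, one giving cisplatin and the other withholding it. That is first a matter of consistent and safe conduct.

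It also reaches the primary endpoint, because withholding is itself a counted event. The Section 8.2 rule is a hard count: more than 5 UTs in the first 10 patients, or more than 11 in 30. A single reclassified patient matters only when the count sits at one of those limits, but there it would decide the conclusion.

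Table 4, immediately above in the same section, avoids the problem. Its renal bands are bounded below inclusively and above exclusively, so the protocol already has a form of wording that leaves no overlap.

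**Working it through.** **Inputs.** Table 5 rows and columns (Section 5.3.2.1), six planned doses (Section 5.3.1.3.1), and the two cisplatin UT criteria (Sections 3.1 and 8.1). The middle row is read as including both printed end values, since nothing excludes them.

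**Step 1. The plan's own design figures.** The exact two-stage binomial probability of concluding unsafe is P(X1 ≥ 6 of 10), plus the sum over x1 ≤ 5 of P(X1 = x1) × P(at least 12 − x1 UTs in the next 20). At a true UT rate of 0.3 this gives 17.7% (4.7% from stage 1). At 0.5 it gives 90.5% (37.7% from stage 1). Section 8.2 states 17% and 90%, which agrees to within one point. These figures take the UT rate as given, so Table 5 does not enter them.

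**Step 2. Cells that apply at each boundary.**

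| Count | Platelets >150 | Platelets 75-149 | Platelets <75 |
|---|---|---|---|
| ANC 0.8 (middle or bottom row) | 100% or 0% | 75% or 0% | 75% or 0% |
| ANC 1.4 (top or middle row) | 100% in both | 100% or 75% | 75% in both |

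The rows conflict in all three columns at ANC 0.8, but in only one at ANC 1.4.

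For platelets of exactly 150 no column applies. The two neighbouring columns agree in the top row (100%) and in the bottom row (0%). They differ, 100% or 75%, only in the 0.8-1.4 row.

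**Step 3. Effect on the UT criteria.** With w doses withheld and k doses given at 75%, the share of the total delivered is (6 − w − 0.25k)/6.

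ANC 0.8 before two doses, with the other four given in full:
- Middle row: w = 0 and k = 0 to 2, depending on platelets. The share is 6/6 = 100% down to (6 − 0.5)/6 = 91.7%. Neither criterion is met.
- Bottom row: w = 2 and k = 0. The share is 4/6 = 66.7%. The criterion of two or more withheld doses is met; the below-66% criterion is not.

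The classification therefore turns entirely on the row chosen, and only through the withheld-dose criterion.

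ANC 0.8 before one dose only, with no other omission: w = 1 gives at most one withheld dose and 5/6 = 83.3%. There is no cisplatin UT on either reading.

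ANC 1.4 or platelets 150 at every dose: at worst w = 0 and k = 6, giving (6 − 1.5)/6 = 75%. There is no cisplatin UT.

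Those two faults combined with one dose withheld for another reason:
- w = 1, k = 4: (6 − 1 − 1)/6 = 66.7%, no UT.
- w = 1, k = 5: (6 − 1 − 1.25)/6 = 62.5%, a UT.

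So they can tip the below-66% criterion only alongside other omissions or reductions.

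**The case against.** The strongest reply is that this will seldom matter. For the overlap alone to create a UT, one patient must have an ANC of exactly 0.8 before at least two of six doses. In the earlier cisplatin trial described in Section 4.2.3, 3 of 36 patients (8%) had two or more doses omitted and another 3 of 36 had one omitted. Exact-boundary cases would be some fraction of such omissions, although adding pembrolizumab could change the rates. This stands, and it is why the effect is described as possible rather than measured.

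A second reply is that such a patient might already be a UT through a grade 3 or 4 adverse event. That may sometimes be so. However, Sections 7.2.1 and 7.2.6 make laboratory values reportable only when the investigator judges them clinically significant, so that route does not reliably replace the withheld-dose criterion. It also leaves the dosing contradiction untouched.

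A third is that a doctor assesses the patient before each dose (Section 5.3.1.3.1). The assessment is required, but nothing there says which row of Table 5 to use.

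Finally, the point rests on single inequality signs in a table read from PDF by a program. There is no evidence of misreading, but the source page should be checked.

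**Conclusion.** Table 5 contradicts itself at ANC 0.8 in every platelet column, and no footnote or other section resolves it. That is an internal inconsistency in an operative dosing rule. It can move a patient between no cisplatin UT and a cisplatin UT under the withheld-dose criterion of Sections 3.1 and 8.1. The ANC 1.4 overlap and the platelet-150 gap are genuine but minor.

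Four stronger readings are tempting and are not supported:
- **All three faults change the number of withheld doses.** Only ANC 0.8 does; the others choose between 100% and 75%.
- **Two withheld doses also breach the dose-total criterion.** They leave 66.7%, which is not below 66%.
- **A fixed share of ANC values is ambiguous.** Any such share depends on reporting precision, which the documents do not give: 2 of 7 values in the 0.8-1.4 band at one decimal, 2 of 61 at two. It would still overstate the conflict at ANC 1.4, and it counts possible values, not patients.
- **The operating characteristics in Section 8.2 are wrong.** They are not affected.

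The conclusion assumes the signs are as printed and uses the endpoint as worded in Sections 3.1 and 8.1. Section 4.2.4.1 words cisplatin failure differently, referring to dose reduction and to omission of more than two doses, and the classification could change under that wording. The number of patients affected cannot be estimated from the documents. The priority is low: worth correcting, but not a threat to the design.

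**What to change.** Check the printed signs in Table 5 against the source page. The sponsor's clinical team should then reconcile the row and column boundaries so that every ANC and every platelet value falls in exactly one cell, for example by using the half-open form of Table 4. Which cell should govern at each boundary is a clinical decision for that team, and none is proposed here.

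The cost is a few inequality signs in one table, carried in an amendment and notified to sites. If patients have already been treated, list any doses decided at ANC 0.8, ANC 1.4 or platelets 150, so that their UT classification can be reviewed consistently. No change to the sample size or decision thresholds is needed.

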5.3.2.2 Pembrolizumab

Adverse events (both non-serious and serious) associated with pembrolizumab exposure may represent an immunologic etiology. These adverse events may occur shortly after the first dose or several months after the last dose of treatment. Pembrolizumab must be withheld for drug-related toxicities and severe or life-threatening AEs as per Table 6 below. See Section 5.5.1 for supportive care guidelines, including use of corticosteroids.

Table 6: Dose Modification Guidelines for Pembrolizumab Drug-Related Adverse Events

General instructions:				
Immune-related AEs	Toxicity grade or conditions (CTCAEv4.0)	Action taken to pembrolizumab	irAE management with corticosteroid and/or other therapies	Monitor and follow-up
Pneumonitis	Grade 2	Withhold	
 Administer corticosteroids (initial dose of 1-2 mg/kg prednisone or equivalent) followed by taper 	
 Monitor participants for signs and symptoms of pneumonitis Evaluate participants with suspected pneumonitis with radiographic imaging and initiate corticosteroid treatment Add prophylactic antibiotics for opportunistic infections
	Grade 3 or 4, or recurrent Grade 2	Permanently discontinue		
Diarrhea / Colitis	Grade 2 or 3	Withhold	
 Administer corticosteroids (initial dose of 1-2 mg/kg prednisone or equivalent) followed by taper 	
 Monitor participants for signs and symptoms of enterocolitis (ie, diarrhea, abdominal pain, blood or mucus in stool with or without fever) and of bowel perforation (ie, peritoneal signs and ileus). Participants with \geq Grade 2 diarrhea suspecting colitis should consider GI consultation and performing endoscopy to rule
	Grade 4	Permanently discontinue		

				
 out colitis. Participants with diarrhea/colitis should be advised to drink liberal quantities of clear fluids. If sufficient oral fluid intake is not feasible, fluid and electrolytes should be substituted via IV infusion.
AST / ALT elevation or Increased bilirubin	Grade 2	Withhold	
 Administer corticosteroids (initial dose of 0.5- 1 mg/kg prednisone or equivalent) followed by taper 	
 Monitor with liver function tests (consider weekly or more frequently until liver enzyme value returned to baseline or is stable
	Grade 3 or 4	Permanently discontinue	
 Administer corticosteroids (initial dose of 1-2 mg/kg prednisone or equivalent) followed by taper 	
Type 1 diabetes mellitus (T1DM) or Hyperglycemia	Newly onset T1DM or Grade 3 or 4 hyperglycemia associated with evidence of β -cell failure	Withhold	
 Initiate insulin replacement therapy for participants with T1DM Administer anti-hyperglycemic in participants with hyperglycemia 	
 Monitor participants for hyperglycemia or other signs and symptoms of diabetes.
Hypophysitis	Grade 2	Withhold	
 Administer corticosteroids and initiate hormonal replacements as clinically indicated. 	
 Monitor for signs and symptoms of hypophysitis (including hypopituitarism and adrenal insufficiency)
	Grade 3 or 4	Withhold or permanently discontinue ¹		
Hyperthyroidism	Grade 2	Continue	
 Treat with non-selective beta-blockers (eg, propranolol) or thionamides as appropriate 	
 Monitor for signs and symptoms of thyroid disorders.
	Grade 3 or 4	Withhold or permanently discontinue ¹		
Hypothyroidism	Grade 2-4	Continue	
 Initiate thyroid replacement hormones (eg, levothyroxine or liothyroinine) per standard of care 	
 Monitor for signs and symptoms of thyroid disorders.
Nephritis	Grade 2	Withhold	
 Administer corticosteroids (prednisone 1-2 mg/kg or equivalent) followed by taper. 	
 Monitor changes of renal function
	Grade 3 or 4	Permanently discontinue		
Myocarditis	Grade 1 or 2	Withhold	
 Administer corticosteroids (initial dose of 1-2 mg/kg prednisone or equivalent) followed by taper 	
 Ensure adequate evaluation to confirm etiology and/or exclude other causes
	Grade 3 or 4	Permanently discontinue		
All other immune-related	Intolerable/ persistent Grade 2	Withhold	
 Based on type and severity of AE administer corticosteroids 	
 Ensure adequate evaluation to

AEs	Grade 3	Withhold or discontinue based on the type of event. Events that require discontinuation include and not limited to: Gullain-Barre Syndrome, encephalitis		confirm etiology and/or exclude other causes		
	Grade 4 or recurrent Grade 3	Permanently discontinue				
1. Withhold or permanently discontinue pembrolizumab is at the discretion of the investigator or treating physician.						
NOTE: For participants with Grade 3 or 4 immune-related endocrinopathy where withhold of pembrolizumab is required, pembrolizumab may be resumed when AE resolves to \leq Grade 2 and is controlled with hormonal replacement therapy or achieved metabolic control (in case of T1DM).						

Dosing of cisplatin and radiation can proceed despite the development of pembrolizumab related adverse events with the exception of the dose modifications described specifically in the sections related to cisplatin and radiation.

Dosing interruptions are permitted in the case of medical / surgical events or logistical reasons not related to study therapy (e.g., elective surgery, unrelated medical events, patient vacation, and/or holidays). Participants should be placed back on study therapy within 3 weeks of the scheduled interruption, unless otherwise discussed with the Coordinating Principal Investigator. The reason for interruption should be documented in the patient's study record.

5.3.3 Timing of Dose Administration

Pembrolizumab should be administered on Day 1 of commencement of chemoradiotherapy after all procedures/assessments have been completed as detailed on the Trial Flow Chart (Section 6.0).

Pembrolizumab 200mg IV will be given in weeks 1, 4, 7, 10, 13, 16 and 19. Treatment may be administered up to 3 days before or after the scheduled day of each cycle due to administrative reasons.

In the event of a treatment delay due to an adverse event outlined in Table 6, patients may resume pembrolizumab within 12 weeks of the due dose so long as the toxicity has resolved to Grade 1 or less and the patient is on a dose of 10mg or less of prednisolone or equivalent. Subsequent dosing of pembrolizumab will continue until week 19, but not beyond this regardless of the total number of doses that the patient has received.

All trial treatments should be administered on an outpatient basis unless discussed with the Principal Investigator/Sponsor.

5.3.4 Radiation Schedule

The information provides detail on the generation of the conventional image guided radiotherapy.

5.3.4.1 Statement of treatment aim and rationale

The aim of this study is to deliver a radical dose of radiotherapy to the entire bladder volume for eligible participants who provide informed consent. A dose of 64Gy in 32 fractions over 6 weeks and 2 treatment days is prescribed.

The radiotherapy plan is used to deliver treatment for fractions 1 to 32 using a standard planning approach with daily image guidance using Cone Beam CT (CBCT).

5.3.4.2 Credentialing

Sites will complete one credentialing case for completion, submission and approval prior to commencement of radiotherapy. Details of the credentialing process are in the Radiation Manual.

5.3.4.3 Treatment Schedule

Radiotherapy will commence according to standard departmental protocols but not more than 42 days after TURBT. If delays of longer than this are anticipated then a second TURBT is permitted to achieve maximum resection of the tumour prior to radiation.

5.3.4.4 Planning Simulation

CT based planning using standard departmental imaging guidelines is required. Scan properties (thickness, width) should enable accurate delineation of all structures and facilitate the construction of high quality transverse, sagittal and coronal plane reconstructions as well as digital reconstructed radiographs (DRRs). Scan thickness and width of equal to or less than 3mm is recommended.

Scan volume should include the entire bladder volume and all relevant organs at risk. It is recommended that scan extents are L4 – ischial tuberosities.

Patient positioning is to be supine using standard departmental guidelines, using appropriate immobilization. Simulation and treatment position must be identical.

An empty bladder is required for all imaging and treatment processes, all participants must void immediately prior to simulation. Where a participant is unable to void or has a residual bladder volume, any further simulation options to ensure a minimum bladder volume are at the prescribing Radiation Oncologist's discretion.

Rectal preparation is not required, however, the rectal cross section at the central CT slice should be <4.0cm in diameter. Where a rectal diameter is >4.0cm, instruct the patient to return to the bathroom and attempt to pass gas or faecal material. Rescan and review the rectal diameter. In cases where the diameter continues to exceed 4.0cm, any further simulation options to reduce the rectal cross-sectional diameter are at the prescribing Radiation Oncologist's discretion.

Surface markers should be placed at a minimum on skin surface to define the CT reference point and marked with a permanent/semi-permanent marker for subsequent identification at the treatment phase. Additional markers along the midline (minimum of two) are required to assist with alignment and markers on the lateral pelvis to assist with correction of rotation are also required. Measurements of all reference and marker points should be recorded.

5.3.4.5 Target volume definitions/Field Borders

5.3.4.5.1 Target Volumes

Target Volumes are defined from the planning CT, these include:

- **Clinical Target Volume (CTV)** - The clinical target volume (CTV) should include the whole bladder, the tumour bed region, the proximal urethra and, in the male patient, if there is involvement of the bladder neck and/or prostatic fossa, the entire prostatic urethra. Patients who have had a previous prostatectomy and bladder neck involvement should have urethra covered for a distance of 2 cm distal to the bladder neck. Any extra-vesical extension (e.g. peri-vesical fat) will be included in the CTV. No attempt will be made to cover nodal groups including first echelon lymph nodes (obturator) in the immediate vicinity of the bladder. Unusual anatomical variations (e.g. cystoceles and diverticula) should be covered. In cases involving the ureteric orifice, the distal ureter should be covered to a distance of 1 cm.
- **Planning Target Volume** - Will be created by a CTV to PTV expansion of
 - Laterally 0.8cm
 - Anteriorly 1.5cm
 - Posteriorly 1.2cm
 - Superiorly 1.5cm
 - Inferiorly 0.8cm

5.3.4.6 Normal tissue contouring

The rectum and right and left femurs must be contoured on the planning simulation CT scan.

Organ at risk delineation and dose constraints include:

Rectum:

- Delineation: Rectal volume to be marked as a solid structure from the upper field border to the lower field border.

Femurs:

- Delineation: Femurs are contoured from acetabulum to a lower extent equal to the most inferior border of the field edge.

5.3.4.7 Dose prescription and Fractionation:

5.3.4.7.1 Total Dose and Dose per Fraction

The total dose prescribed is 64Gy.

Dose fractions of 2.00Gy are required to be delivered once daily for 32 fractions, 5 fractions/week. In the event of a treatment interruption for any reason, the missing dose fraction(s) should be made up according to the instructions provided in 5.3.4.7.2.

The reason for any treatment interruption must be documented.

5.3.4.7.2 Treatment Duration

The total treatment duration is 6 weeks and 2 treatment days. Treatment should be completed from commencement unless severe acute toxicity is observed.

Where an interruption occurs:

- A minor radiation protocol deviation is recorded when the treatment extends from 6.4 up to 7 weeks
- A major radiation protocol deviation is recorded when the treatment extends beyond 7 weeks

Strategies for managing treatment interruptions (planned or unplanned) include

- Treating 6 fractions per week preceding or following a week where 4 fractions are delivered
- Treating twice a day with a 6hr treatment interval where treatment is not possible on a scheduled day
- Substituting a weekend day for a week day where treatment is not possible on a pre-programmed day
- Note: No more than 6 fractions may be given in any one week.
- Note: The reason for any treatment interruption must be documented.

